#### 10.4.2 ANALYSIS OF THE PRIMARY ENDPOINT(S)

The primary outcome of the feasibility is enrollment ( $\geq 60\%$ ). A one-sample binomial test will be used to compare the observed enrollment percentage to 60%.

Enrollment (primary): Number of patients enrolled divided by the number of eligible patients approached

Retention: The percentage of patients and providers who complete baseline and follow-up questionnaires.

Acceptability: Mean post-treatment patient and provider ratings  $\geq 3.5/5$  on intervention acceptability, feasibility, and appropriateness (psychometrically validated measure; Table 2), and a brief semi-structured interview to explore factors associated with acceptability.

---

#### 10.4.3 ANALYSIS OF THE SECONDARY ENDPOINT(S)

We will describe pre-post changes in the patient-reported outcome variables related to a future trial using univariate and bivariate statistics. Our chief goals will be to estimate the standard deviations of our key variables for use in planning future studies. We will examine, through the use of t-tests, whether pre-post changes in the mPal differ significantly from pre-post changes in the control group. If our intervention is successful, we would expect to see significantly greater improvement over time in our effectiveness outcomes (PC knowledge, motivation) in treatment vs. control. We will also examine correlations between changes in these measures and PC referrals; we expect changes in PC knowledge and motivation variables will be positively correlated with changes in PC referrals within both treatment and control groups.

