#### Primary Objectives

1. Evaluate mPal’s feasibility and acceptability. We hypothesize we will be able to enroll  $\geq 60\%$  of asLC patients we approach (primary feasibility outcome), retain  $\geq 60\%$  for one-month follow-up, and achieve mean patient and provider feasibility ratings of  $\geq 3.5/5$ . For acceptability, we hypothesize we will be able to achieve mean patient and provider acceptability ratings of  $\geq 3.5/5$ . We anticipate qualitative data (n = 40 mPal patient interviews; n = 6 provider interviews) will further support the ease of use and clinical value of mPal.
2. Obtain preliminary data on effectiveness and equity outcomes for a planned trial. In line with best practices for pilot studies, we are not testing formal hypotheses for effectiveness outcomes; however, we will measure patient and provider PC knowledge and motivation and PC referrals, which we expect will improve with mPal. For equity outcomes, we will explore whether mPal appears similarly effective for patients with different characteristics (e.g., rural vs. urban, health literacy, income, race) by analyzing survey and semi-structured intervention data from mPal patients (n = 40).

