#### 4.2 SCIENTIFIC RATIONALE FOR STUDY DESIGN

In line with best practices for pilot studies, we are testing feasibility, not formal hypotheses surrounding effectiveness outcomes. We are not randomizing provider and system-level strategies because 1) we do not plan to randomize providers in our next trial (rather, clinics will be randomized to start mPal at different times through a stepped-wedge design); and 2) intervention contamination would occur within the clinic.

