## 6.3 MEASURES TO MINIMIZE BIAS: RANDOMIZATION AND BLINDING

This is a randomized controlled trial design (patient-level randomization). Study staff and patients will not be blinded to allocation; however, study staff and patients will not know allocation until after a patient has completed the baseline questionnaire. The statistician will generate the randomization table, which will be implemented through REDCap.

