## 9 STUDY ASSESSMENTS AND PROCEDURES

## 9.1 ENDPOINT AND OTHER NON-SAFETY ASSESSMENTS

**Screening.** We will build a master list form in REDCap linking patient names, MRNs, and study IDs. We will build a separate REDCap form for screening. The eligibility screening form will include patient screener ID, date screened, date must be enrolled by (21 day window), eligibility criteria (e.g., performance status, time on cancer treatment, age, etc.), whether the patient is being rescreened for eligibility, and, if rescreened, the last date of screening. If deemed potentially eligible, additional fields will appear in the eligibility database for tracking dates of upcoming appointments and contact with patients. Patients must be enrolled within 21 days of screening or else they will need to be rescreened.

**Administration of Questionnaires.** Patient-reported measures related to a future efficacy trial and of treatment processes were chosen based on their validity and sensitivity to change in cancer patients and recommendation for clinical trials. These measures will be completed by patients pre-intervention (TP0), ~4 weeks after baseline (T1), and post-intervention (~8-weeks after T0; TP2) on paper, online (REDCap), or by phone. For patients who use MyChart®, a link to the REDCap survey will be provided through a study research message delivered in MyChart®. Patients will use a participation ID on their questionnaires. If more than 30 days pass between baseline and participant viewing the mPal tool, key sections (e.g., palliative care knowledge, palliative care use) of the baseline questionnaire will be re-administered prior to viewing mPal. See **Table 2** for a list of measures to be administered, psychometric properties, assessment schedule, and role in analysis plan. All patient-reported measures will be entered in REDCap in the REDCap project built for those patients who enroll.

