**Table 2. Aim 1 and 2 Measures**

Construct	Description	Data Sources	Level		Schedule
			Pt	Pv/Sy	
Aim 1. Implementation Outcomes					
Feasibility	FIM  : 4 item implementation measure of intervention feasibility ( $\alpha = .89$ ); Individual interviews (pts, pvs)	Survey; interviews	X	X	mPal Patients: T1 Providers: T3
Acceptability	AIM  : 4 item implementation measure of intervention acceptability ( $\alpha = .85$ ) individual interviews (pts, pvs)	Survey; interviews	X	X	mPal Patients: T1 Providers: T3
Aim 2. Effectiveness and Equity Outcomes related to Planned Future Trial					
PC referral	Proportion of patients in each arm who receive a referral to PC within 1-month (survey) and 3-months (EHR) post-mPal intervention	EHR, Survey	X	X	Patients: T2 (survey); System: 3-months post intervention (EHR)
PC knowledge	HINTS PC  : 10 items; assesses self-reported PC knowledge and PC perceptions. PACKS	Survey	X	X	Patients: T0, T1 (mPal only), T2 Providers: T0, T1, T3
Motivation to use PC	PCAS-9  : 9 items; assesses emotional, cognitive, and behavioral components of motivation to use PC ( $\alpha$ 's = .70-.90)	Survey	X	X	Patients: T0, T1 (mPal only), T2 Providers: T0, T1, T3
Opportunities to use PC	5 items; perceived ability to access PC. Based on preliminary study and literature. 	Survey,	X	X	Patients: T0, T2 Providers: T0, T3
PC discussion	2 survey items; Interview questions to supplement (experiences discussing PC during clinical encounters, quality of discussion, how mPal was used)	Survey, depth interviews	X	X	Patients: T0, T2 Providers: T0, T3
Demographics	15 items; sociodemographics, health literacy  (pts), PC training (providers)	Survey	X	X	Patients: T0 Providers: T0
Equity	Characteristics of mPal patients who do/do not seek PC referral and do/do not show knowledge increase; Interview with those who do/do not use PC; barriers	Survey, interviews	X	X	mPal Patients: T2, 3m post intervention

Note. Pt = Patient; PV = provider; Sy = System; T = timepoint; T0 = baseline; T1 = post mPal app viewing or knowledge check (pt assessment); post webinar viewing (providers); T2 = 8-week follow-up (pt assessment); T3 = post-patient-level intervention period (for providers)

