### 10.4 STATISTICAL ANALYSES

#### 10.4.1 GENERAL APPROACH

We will use descriptive statistics (means, standard deviations, median, range) to examine the distribution of continuous variables. We will calculate 95% CIs for each of the feasibility measures to determine the range of estimates that are consistent with our data.

We will use one-sample negative binomial probabilities and tests of binomial proportions to compare to hypothesized values. We will summarize reasons for ineligibility and refusal and compare patients who drop out or do not adhere by demographic and clinical characteristics. Ordinal scaled variables such as feasibility and acceptability will be compared between groups

before and after baseline (as well as change from baseline) using the Wilcoxon Rank Sum statistic. Within group comparison of the pre versus post baseline measures will be evaluated using the Wilcoxon Signed Rank statistic.

We will use qualitative methods to analyze patient and provider feedback from the exit interviews and descriptive statistics to summarize participants' acceptability, feasibility, and appropriateness ratings of the intervention. The interviews will be transcribed verbatim and managed in ATLAS.ti or other qualitative software for analysis. The PI and study coordinator will code interviews by domains (e.g., perceived impact of mPal on clinical care, barriers, facilitators to using mPal, suggested changes to improve equity of mPal). Data will be analyzed using thematic content analysis to describe perceptions.

Statistical significance will be indicated by  $p < .05$ .

---

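### Section 10.4.3 compares the arms by unadjusted t-tests on change, worded as significance tests; T0-adjusted differences with 95% CIs would suit the stated purpose and usually be more precise

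*Combined protocol and SAP*

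**What the plan says.** Section 10.4.3 gives estimation of standard deviations for later trials as its chief goal. It then plans a between-arm comparison: "We will examine, through the use of t-tests, whether pre-post changes in the mPal differ significantly from pre-post changes in the control group". It adds that a successful intervention should show a significantly larger improvement in knowledge and motivation than control. No covariate is named.

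The objectives take a different line. The synopsis says "we are not testing formal hypotheses for effectiveness outcomes", Section 3 repeats this, and Section 4.2 says "we are testing feasibility, not formal hypotheses surrounding effectiveness outcomes".

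On intervals, Section 10.4.1 says "We will calculate 95% CIs for each of the feasibility measures". None is stated for a difference between arms. The same section sets p < .05 without limiting it to the feasibility tests.

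Three further statements bear on how change is defined:

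- Section 10.4.1 compares ordinal variables between groups "before and after baseline (as well as change from baseline) using the Wilcoxon Rank Sum statistic". It names feasibility and acceptability as examples. Table 2 schedules both as "mPal Patients: T1 Providers: T3".
- Section 9.1 provides for a second baseline: "If more than 30 days pass between baseline and participant viewing the mPal tool, key sections (e.g., palliative care knowledge, palliative care use") are given again before the tool is viewed.
- Section 6.3 says that "study staff and patients will not know allocation until after a patient has completed the baseline questionnaire".

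Table 2 schedules PC knowledge and motivation for patients at T0 and T2 in both arms, and at T1 in the mPal arm only.

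**The concern.** Aim 2 is there to supply planning data for the next trial. For that purpose the useful output is an estimated arm difference with an interval, together with the SDs and the T0-T2 correlation. A significance statement gives less, and it invites a reading that the objectives disclaim. The sample size of 80 rests on feasibility estimates (Section 10.2), so a non-significant t-test would say little about whether mPal works.

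Precision that the data could provide is also left unused. T0 scores exist in both arms, and a change score subtracts T0 with a fixed weight of one, whatever the actual relation between T0 and T2.

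Finally, 10.4.3 does not say which value is *pre* when Section 9.1 has produced two, nor whether the Wilcoxon change comparison of 10.4.1 also applies to these scales.

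**Working it through.** **No figure to reproduce.** The documents give no effect size, SD, power or precision target for the arm comparison.

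**Inputs from the documents.** 40 patients per arm; a retention target of 60%, so 0.60 × 40 = 24 per arm at that target; T0 and T2 scores in both arms (Table 2); T2 at 8 ± 3 weeks after T0 (Section 1.2).

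**Assumptions.** The T0-T2 correlation ρ and the ratio k = SD(T2)/SD(T0) are not in the documents, so ranges are shown. SD(T0) is set to 1.

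**Formulas.**
- Variance of the change score: 1 + k² − 2ρk.
- Residual variance after T0 adjustment: k²(1 − ρ²).
- 95% half-width: t(0.975) × √(2 × variance / n), with 2n − 2 df for change and 2n − 3 df for ANCOVA. The ANCOVA variance is also multiplied by 1 + 1/(2n − 4) for chance baseline imbalance.

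**Worked case, n = 40, k = 1, ρ = 0.5.** Change: variance 1.00, half-width 1.991 × √(2 × 1.00/40) = 0.445. ANCOVA: variance 0.75, half-width 1.991 × √(2 × 0.75 × (1 + 1/76)/40) = 0.388. The reduction is 1 − 0.388/0.445 = 13%.

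**Half-widths in SD(T0) units, change vs ANCOVA.**

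| n per arm | k | ρ = 0.3 | ρ = 0.5 | ρ = 0.7 | ρ = 0.8 | ρ = 0.9 |
|---|---|---|---|---|---|---|
| 40 | 0.8 | 0.480 vs 0.342 | 0.408 vs 0.310 | 0.321 vs 0.256 | 0.267 vs 0.215 | 0.199 vs 0.156 |
| 40 | 1 | 0.527 vs 0.428 | 0.445 vs 0.388 | 0.345 vs 0.320 | 0.282 vs 0.269 | 0.199 vs 0.195 |
| 40 | 1.25 | 0.599 vs 0.534 | 0.510 vs 0.485 | 0.401 vs 0.400 | 0.334 vs 0.336 | 0.249 vs 0.244 |
| 24 | 1 | 0.688 vs 0.561 | 0.581 vs 0.509 | 0.450 vs 0.420 | 0.368 vs 0.353 | 0.260 vs 0.256 |
| 24 | 1.25 | 0.782 vs 0.701 | 0.666 vs 0.637 | 0.524 vs 0.525 | 0.436 vs 0.441 | 0.325 vs 0.320 |

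With k = 1 and ρ = 0.3/0.5/0.7, ANCOVA is 19/13/7% narrower at 40 per arm and 18/12/7% narrower at 24. The gain disappears near k = 1.25, ρ = 0.8 because the regression slope is ρk = 1 there. The change score is then already the best linear adjustment, and ANCOVA only pays its degree of freedom. In simulations with equal SDs (5,000 trials per cell, ρ 0.3 to 0.9, both sample sizes), coverage was 94% to 96% for both methods.

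**What a p-value would tell.** For an assumed difference of 0.5 SD with k = 1 and ρ = 0.5, normal-approximation power of the change t-test is 61% at 40 per arm (0.5/√(2/40) − 1.96 = 0.28) and 41% at 24. With T0 adjustment it is 73% and 52%.

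**Which value is *pre*.** The T2 window is 5 to 11 weeks, or 35 to 77 days from T0. From a baseline repeated on day 31 it would be 4 to 46 days. The repeat is triggered by a delay in viewing mPal, so it can arise only in the mPal arm, after allocation is known. If the repeated value were used, the arm difference in change would move by (share of mPal patients repeated) × (drift before viewing). With an assumed share of 10% to 50% and drift of 0.1 to 0.3 SD, that is 0.1 × 0.1 = 0.01 to 0.5 × 0.3 = 0.15 SD. The upper end is unlikely: T1 is set at about 3 to 4 weeks and follows viewing, so most patients should view within 30 days.

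**Referral.** Table 2 already plans proportions by arm. As an illustration, assume 6/40 (15%) referred under usual care; Section 2.1 gives under 15% for receipt of PC, not referral. Newcombe 95% CIs for the risk difference are then −8 to 27 points for 10/40 in mPal, −3 to 32 for 12/40 and 5 to 42 for 16/40.

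**The case against.** The strongest reply is that this is an exploratory pilot analysis using a valid test. No go/no-go rule depends on it, SD estimation is the declared goal, and the planned univariate and bivariate summaries could include the T0-T2 correlation. CIs are not excluded, and one could be computed from the planned means and SDs. All of this stands, and it limits the weight of the point. It does not remove the mismatch between the significance wording and the objectives, and it argues for stating the interval.

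The second reply, that the gain rests on an unknown ρ and unknown SDs, also stands; the table shows where the gain is negligible or reversed.

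A reader might infer more than the documents support:

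- *The t-test on change is biased.* It is not; randomisation makes it valid.
- *The arms will have different baselines.* Section 9.1 labels T0 as pre-intervention and Table 2 schedules T0 and T2, so T0 is the natural default. Comparability is lost only if the repeat is used. Motivation is not among the repeated sections named as examples.
- *The plan prescribes two contradictory tests.* The Wilcoxon examples are feasibility and acceptability, which patients rate only in the mPal arm, so no between-arm patient comparison is possible for them. Section 10.4.3 names knowledge and motivation for the t-tests, and the specific section would normally govern. The overlap is an ambiguity.
- *The equity aim is unsound.* Reach, and the characteristics of mPal patients who do or do not seek referral, are proper questions within one arm. Only the claim of similar effectiveness across groups would need the control arm, and that is a matter of wording.

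**Conclusion.** The point holds as an improvement worth making to a secondary analysis. The plan tests change between arms with significance wording that its objectives disclaim, states no interval for that difference, and leaves unused T0 data that would usually sharpen the estimate. Under equal SDs and ρ of 0.3 to 0.7, the interval would be about 7% to 19% narrower at 40 per arm. The advantage is larger if the T2 SD is smaller than the T0 SD (20% to 29% at a ratio of 0.8 over the same ρ). It is small or absent if the T2 SD is larger and the correlation high. These sizes rest on assumed values; the mismatch in wording and the missing interval do not. The definition of *pre* and the choice of a single method need only a clarifying sentence each. Enrollment, the sample size of 80 and the feasibility conclusions are not affected.

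**What to change.** 1. In 10.4.3, for each PC knowledge and motivation scale score, replace the t-test with ANCOVA of the T2 score on arm and T0 score. Report the adjusted difference with its 95% CI, the SDs and the T0-T2 correlation, labelled as descriptive planning estimates. Remove the significance wording and state that the p < .05 line in 10.4.1 does not apply to these outcomes.
2. Define *pre* as the T0 value obtained before allocation, in both arms. Report any repeat baseline under Section 9.1 descriptively, for mPal patients only.
3. State that this is the only between-arm analysis for these scales, in place of any Wilcoxon change comparison under 10.4.1.
4. Keep the referral proportions by arm and add the risk difference with a 95% CI.
5. Optional and minor: reword the similar-effectiveness phrase in Objective 2 towards reach, as Section 4.1 already does.

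The cost is SAP wording only, with no new data, visits or patients. ANCOVA uses one degree of freedom, assumes a roughly linear T0-T2 relation, and brings little or no gain in part of the plausible range.

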**Study Description and Objectives:**

This is a pilot RCT (40 patients mPal; 40 patients usual care; 6 providers not randomized) to test the feasibility and acceptability of a multilevel implementation strategy for outpatient palliative care (PC).

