### 3 OBJECTIVES

#### PRIMARY OBJECTIVES

1. **Evaluate mPal's feasibility and acceptability.** We hypothesize we will be able to enroll  $\geq 60\%$  of asLC patients we approach (primary feasibility outcome), retain  $\geq 60\%$  for one-month follow-up, and achieve mean patient and provider feasibility ratings of  $\geq 3.5/5$ . For acceptability, we hypothesize we will be able to achieve mean patient and provider acceptability ratings of  $\geq 3.5/5$ . We anticipate qualitative data ( $n = 30-40$  mPal patient interviews;  $n = 6$  provider interviews) will further support the ease of use and clinical value of mPal.
2. **Obtain preliminary data on effectiveness and equity outcomes for a planned trial.** In line with best practices for pilot studies, we are not testing formal hypotheses for effectiveness outcomes; however, we will measure patient and provider PC knowledge and motivation and PC referrals, which we expect will improve with mPal. For equity outcomes, we will explore whether mPal appears similarly effective for patients with different characteristics (e.g., rural vs. urban, health literacy, income, race) by analyzing survey and semi-structured intervention data from mPal patients ( $n = 30-40$ ).

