### 10.2 SAMPLE SIZE DETERMINATION

The sample size of 80 patients is based on the goal of estimating the probabilities and means for 2 feasibility outcome measures (enrollment  $\geq 60\%$  [primary],  retention  $\geq 60\%$ ). We will use feasibility outcomes to inform a future trial. For structured interviews, we anticipate we will be able to identify key themes with 20 interviews.

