### 10.3 POPULATIONS FOR ANALYSES

The patient sample ( $n = 40$  mPal;  $n = 40$  usual care) will be used to analyze feasibility and acceptability data and describe pre-post changes in patient-reported outcomes. The provider sample ( $n = 6$ ) will be used to demonstrate feasibility of measurement collection.

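### Change-score t-tests and a survey-based 1-month referral leave patients without T2 unscored; a T0-adjusted model and the dated EHR referrals already collected would serve better

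*Combined protocol and SAP*

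**What the plan says.** Section 10.4.3 compares the arms on knowledge and motivation as follows: "We will examine, through the use of t-tests, whether pre-post changes in the mPal differ significantly from pre-post changes in the control group". Section 10.4.1 adds Wilcoxon tests, including on change from baseline, for ordinal variables; these too need both values. Table 2 schedules knowledge and motivation at T0 and T2 in both arms and at T1 in mPal only, so a control patient without T2 has no post-baseline score. Section 10.3 nonetheless names the whole 40 + 40 sample to "describe pre-post changes in patient-reported outcomes".

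For palliative care referral, Table 2 defines a proportion of patients in each arm, taking the 1-month figure from the survey and the 3-month figure from the EHR: "Patients: T2 (survey); System: 3-months post intervention (EHR".

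Section 3 aims to "retain $\geq 60\%$ for one-month follow-up". Section 10.4.2 defines retention as "The percentage of patients and providers who complete baseline and follow-up questionnaires", and Section 4.4 makes T2 the assessment that completes a patient's participation.

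Sections 8.2 and 8.3 describe withdrawal, investigator discontinuation and loss to follow-up, and Section 11.2.1 expects deaths from disease. No section says how a patient without T2 is handled in the T2 outcomes. The only related analysis is the comparison of dropouts by demographic and clinical characteristics in Section 10.4.1.

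**The concern.** A change score exists only for patients who return T2. Randomisation makes the arms comparable at T0, but the patients who return may not be. If returners differ from non-returners on T0, and do so differently by arm, the change-score comparison carries that T0 imbalance, because the change also contains regression to the mean. An arm-specific route is conceivable: only mPal patients receive the education and screener, and Section 11.1.1 names an initial negative reaction in people with misperceptions as a possible risk.

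The 1-month referral proportion has a separate problem. Its denominator reads as all patients in the arm, but its source is a survey that non-returners do not complete, so as planned they count as neither referred nor not referred.

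At stake is the preliminary effectiveness signal carried into the planned trial. Section 10.4.3 looks for significant differences between arms and Section 10.4.1 sets p < .05, so these comparisons will be read as evidence even though the trial is a pilot.

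**Working it through.** **1. How many patients could lack T2.** Sections 10.2 and 10.3 give 80 patients, 40 per arm. Section 10.2 states no precision, power or dropout allowance ("The sample size of 80 patients is based on the goal of estimating the probabilities and means for 2 feasibility outcome measures"), so there is no derivation to reproduce beyond 40 + 40 = 80. At the 60% retention limit, 0.60 × 80 = 48 patients have T2 and 32 do not, or 24 and 16 per arm if loss is equal. This takes the one-month follow-up in the objective to be T2, which Section 4.4 supports but the objective does not state.

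**2. Bias of the change-score difference.** The documents give no effect size, SD or dropout pattern, so everything in this step is assumed. In SD units:
- T0 ~ N(0,1); T2 = ρ·T0 + √(1−ρ²)·e + 0.5 in the mPal arm.
- Probability of returning T2 = expit(logit(base) + slope·T0), with base and slope set by arm.

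Expected bias of the returners-only change difference = −(1−ρ) × (mean T0 of mPal returners − mean T0 of control returners).

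| Assumed dropout (ρ = 0.5) | Mean T0, mPal returners | Mean T0, control returners | Bias (SD) |
|---|---|---|---|
| Base 60% mPal, 80% control; no T0 dependence | 0 | 0 | 0 |
| Base 60% and slope 1 in both arms | 0.35 | 0.35 | 0 |
| Base 80% both; slope 0.5 in mPal only | 0.10 | 0 | −0.05 |
| Base 60% mPal, 80% control; slope 0.5 in both | 0.19 | 0.10 | −0.05 |
| Base 60% mPal, 80% control; slope 1 in both | 0.35 | 0.20 | −0.07 |
| Base 60% mPal, 80% control; slope 1 in mPal only | 0.35 | 0 | −0.17 |

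The last row is steep: an mPal patient 1 SD below mean T0 knowledge returns with probability 36%, one 1 SD above with 80%. Simulation of that row (40 per arm, 4,000 runs) gives a mean change-score difference of 0.33 against the true 0.50, with SD 0.27, so the bias is 0.17/0.27 ≈ 0.6 standard errors. With ρ = 0.3 and 0.7 the means are 0.25 and 0.40. Lowering control retention to 60% leaves the bias at −0.17, so unequal loss is not needed for it; nor is unequal loss sufficient, as the first row shows.

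**3. Conditioning on T0.** Regressing T2 on arm and T0 in the same simulated data gives a mean of 0.50 in every row above. In the steep row its SD is 0.24 against 0.27, and it was also more precise in the rows with no bias.

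**4. What T0 cannot repair.** If loss depends on the change itself, bias ≈ (fraction lost × gap between returners and the lost) in mPal minus the same product in control. With 40% lost in each arm and an assumed gap of 0.5 SD of change in mPal only, this is 0.4 × 0.5 = 0.20 SD. A sensitivity analysis is needed for this.

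**5. One-month referral by survey alone.** Illustration: 24 of 40 return and 6 (an assumed count) report a referral. Among returners this is 6/24 = 25%; with non-returners as no, 6/40 = 15%; with non-returners as yes, (6 + 16)/40 = 55%. This spread applies only if the survey is the sole source. Section 9.1 also collects dated palliative care referrals from the EHR for up to 12 months after enrolment, from all patients who consent.

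**The case against.** Much can be said for the plan. Objective 2 disclaims formal effectiveness hypotheses, and the primary endpoint, enrolment, does not depend on T2. Section 8.1 keeps assessing patients who stop the intervention but stay in the study, so someone put off by the education need not lose T2. Section 8.2 lets hospitalised patients continue assessments, Section 8.3 requires at least three contact attempts, and Section 11.1.1 calls negative reactions rare and mild. Reasons for withdrawal are recorded and dropouts are described.

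These points stand and limit the weight. They also rule out three stronger readings:
- A reader might infer that lost patients cannot be scored on referral at all. They can: EHR referrals are dated, and the 3-month EHR endpoint does not use T2.
- A reader might take 40% loss as expected. It is the loss at which a feasibility floor is still met, not a forecast.
- A reader might take the −0.17 SD as the likely bias. It comes from a steep, one-arm assumption; milder ones give a third of it or nothing.

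What the objection does not supply is a rule for deaths, withdrawals and losses in the T2 outcomes, or a reason to prefer the change-score t-test. The T0-conditioned estimate was unbiased and more precise in every scenario tried, including those where the t-test was also unbiased.

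**Conclusion.** The point holds in limited form and should be acted on. The named tests use only patients with both T0 and T2, and the 1-month referral depends on returning the T2 survey, so up to 32 of 80 patients could go unscored with the retention target met. That the t-test drops these patients is inferred from how it works; the plan itself is silent. Bias in the knowledge and motivation comparison is possible, ranging from 0 to −0.17 SD against an assumed effect of 0.5 SD at correlation 0.5. The dropout patterns, effect and correlation are all assumptions. The documents do not show that bias will occur. For referral the gap is narrower: suitable data are collected, but the plan does not use them for the 1-month measure. Enrolment and 3-month EHR referral are untouched.

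**What to change.** **Knowledge and motivation (Section 10.4.3).** Replace the change-score t-test with a T0-adjusted or likelihood-based model of T0 and T2 that includes all randomised patients with T0. State that the estimand concerns patients alive at T2, or say otherwise how deaths are treated, so that the model does not silently extrapolate scores beyond death. Report missing T2 by arm and reason. Add one sensitivity analysis for missing T2, such as setting it equal to T0 in both arms, and do not use that analysis to estimate the SDs: it adds zero changes, and estimating SDs is the section's chief goal.

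**One-month referral (Table 2).** Score every randomised patient from the dated EHR referrals. Define time zero identically in both arms, for example randomisation, because Table 2 counts from the mPal intervention and usual-care patients have no such date. Count death or loss without a recorded referral as no referral. Keep the T2 survey item as supportive.

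**Cost.** Plan wording and modest programming; no new data. The model assumes that dropout is explained by T0 and arm. EHR dates may miss referrals made outside the centre. Section 9.1 allows mPal to be viewed more than 30 days after baseline, so a window counted from randomisation can include time before viewing; its length should be chosen with that in mind.
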